5.5.3 Treatment Stoppage Rules For Toxicity

If any observed toxicity at least possibly related to ficlatuzumab and/or cetuximab prevents dosing within the scheduled study visit window, the dose for that study visit will be skipped and the next study drug administration will occur at the next scheduled dose. If a ficlatuzumab-related toxicity results in 2 consecutive missed doses, the ficlatuzumab will be discontinued permanently. However, if in the investigator's opinion there is evidence of clinical benefit, a subject with 2 consecutive missed doses may resume treatment after the AE has resolved to the minimum specifications in Table 4A or Table 4B. Contact the Sponsor-Investigator for consensus on subsequent treatment.

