5.5.4 Treatment Interruption for Interstitial Lung Disease

In the event of acute onset (grade \geq 2) or worsening pulmonary symptoms which are not thought to be related to underlying cancer, both cetuximab and ficlatuzumab should be interrupted and a prompt investigation of these symptoms should occur. Neither ficlatuzumab nor cetuximab retreatment should occur until these symptoms have resolved to grade 1. If interstitial lung disease is confirmed, both cetuximab and ficlatuzumab should be discontinued permanently and the patient should be treated appropriately.

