5.5.8 Cetuximab Infusion Reaction

A cetuximab infusion reaction will be managed as described in Table 6 below. If there is any question as to whether an observed reaction is an infusion reaction of Grades 1-4, [name] should be contacted immediately to discuss and grade the reaction.

Should an infusion reaction occur, retreatment will be managed as follows: Once a cetuximab infusion rate has been decreased due to an infusion reaction, it will remain decreased for all subsequent infusions. If the subject has a second infusion reaction with the slower infusion rate, the infusion should be stopped, and the subject should receive no further cetuximab treatment. If a subject that experienced an initial cetuximab infusion reaction experiences a Grade 3 or 4 infusion reaction at any time, the subject should receive no further cetuximab treatment.

Table 6: Management of Cetuximab Infusion Reaction

| Grade | Management |
|--|--|
| Grade 1: Transient flushing or rash; drug fever < 38° C (< 100.4° F) | For mild infusion reactions manifesting only as delayed drug fever, consider administering prophylactic antihistamine medications for subsequent doses. Maintain the cetuximab dose but slow the infusion rate by 50%. Acetaminophen or a non-steroidal anti-inflammatory drug (NSAID) may be administered prior to subsequent cetuximab infusions, if not otherwise contraindicated in subjects. |
| Grade 2: Rash; flushing; urticaria; dyspnea; drug fever ≥ 38° C (≥ 100.4° F) | For moderate infusion reactions manifesting only as delayed drug fever, slow the infusion rate for cetuximab by 50%, and consider administration of antihistamine medications and/or steroidal medications. Maintain the cetuximab dose. Acetaminophen or a non-steroidal anti-inflammatory drug (NSAID) may be administered prior to subsequent cetuximab infusions, if not otherwise contraindicated in subjects. |
| Grade 3: Symptomatic bronchospasm with or without urticaria; parenteral medication(s) indicated; allergy- related edema/angioedema; hypotension | Severe infusion reactions requires immediate interruption of cetuximab infusion and permanent discontinuation from further treatment with cetuximab. Appropriate medical therapy including epinephrine, corticosteroids, diphenhydramine, bronchodilators, and oxygen should be available for use in the treatment of such reactions. Subjects should be carefully observed until the complete resolution of all signs and symptoms. |

| Grade 4: | NO FURTHER CETUXIMAB |

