12.2 Description of Adverse Event Reporting Procedures

Adverse events will be recorded in the adverse events record form in the UACC OnCore CRM and reviewed by the local Principal Investigator. All Adverse Events as defined in this section will be collected starting on Cycle 1, Day 1 must be recorded. AEs will be followed per the details indicated in protocol Section 8.5.1. Only AEs meeting one of the following criteria will be entered into the OnCore CRM study database:

- Any AE that is Grade 3 or higher, regardless of relationship to the study drug
- Any AE that results in submission of a Serious Adverse Event (i.e., hospitalization for a non-serious grade AE)
- Any intolerable (per the opinion of the treating investigator) Grade 2 AE
- Any Grade AE resulting in a dose reduction of ficlatuzumab or cetuximab
- Any Grade 2 laboratory or vital sign values that are deemed clinically significant by the treating investigator
- Any Grade AE in the following categories of interest:
 - o Rash
 - Diarrhea
 - o Edema, peripheral
 - o Edema, head, face and neck
 - o Hypoalbuminemia

All adverse events will be classified using either the MedDRA term or NCI Common Terminology Criteria for Adverse Events (CTCAE) version 4.0 and will address:

- Grade
- Relationship to ficiatuzumab (not related, unlikely, possible, probable, definitely)
- Relationship to cetuximab (not related, unlikely, possible, probable, definitely)

- Causality other than study drug (disease related, concomitant medication related, intercurrent illness, other)
- Date of onset
- Date of resolution
- Frequency of event (single, intermittent, continuous)
- Event outcome (resolved, ongoing, death)
- Action taken with ficlatuzumab (none, held, dose reduced, discontinued, medication given)
- Action taken with cetuximab (none, held, dose reduced, discontinued, medication given)

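### Section 12.2 has a database-entry trigger for AEs that reduce a dose but none for AEs that hold or stop a drug, so some Grade 1 events that end a drug are left out and capture at Grade 2 rests on investigator judgment

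*Combined protocol and SAP*

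**What the plan says.** Section 12.2 (Description of Adverse Event Reporting Procedures) first says that all AEs from Cycle 1 Day 1 must be recorded, then restricts entry: "Only AEs meeting one of the following criteria will be entered into the OnCore CRM study database". The six criteria are:

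1. "Any AE that is Grade 3 or higher, regardless of relationship to the study drug".
2. An AE of any grade that is submitted as an SAE.
3. "Any intolerable (per the opinion of the treating investigator) Grade 2 AE".
4. "Any Grade AE resulting in a dose reduction of ficlatuzumab or cetuximab".
5. Grade 2 laboratory or vital sign values that the investigator considers clinically significant.
6. Any grade of rash, diarrhea, peripheral edema, head/face/neck edema or hypoalbuminemia.

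For each AE the same section asks for "Action taken with cetuximab (none, held, dose reduced, discontinued, medication given", with a parallel field for ficlatuzumab.

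Three rules elsewhere end a drug without a Grade 3 threshold:

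- Section 5.5.8, on a second infusion reaction at the slower rate: "the infusion should be stopped, and the subject should receive no further cetuximab treatment".
- Section 5.5.4: "If interstitial lung disease is confirmed, both cetuximab and ficlatuzumab should be discontinued permanently".
- Section 5.5.3: "If a ficlatuzumab-related toxicity results in 2 consecutive missed doses, the ficlatuzumab will be discontinued permanently", with an exception where there is evidence of clinical benefit.

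**The concern.** Hold, dose reduction and discontinuation are separate codes in the action-taken field, so the dose-reduction criterion cannot be read as covering the other two. The form can code a discontinuation, but nothing in the list requires the event that caused it to be entered. Reduction, the milder consequence, is an objective trigger at any grade; stopping the drug is not a trigger at all.

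Describing toxicity is a secondary objective (Section 2.2). Sections 10.4.1 and 10.6 plan AE proportions by CTCAE grade with exact 95% confidence intervals, and the DSMB reviews AEs every six months (Section 11.4). If the list is followed as written, an AE that ended a drug can be absent from the data behind all of these.

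**Working it through.** No figure in the documents bears on this, so the check is a comparison of texts. Each rule in Sections 5.4 and 5.5 that holds or ends a drug was set against the six criteria, asking whether a Grade 1 or 2 event can trigger the rule without meeting any of them.

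| Event | Rule and consequence | Entered under 12.2? |
|---|---|---|
| Second infusion reaction, Grade 1 (flushing or low drug fever, no rash) | 5.5.8: cetuximab ends | No, unless an SAE |
| Second infusion reaction, Grade 2 | 5.5.8: cetuximab ends | Only if intolerable, an SAE, entered as rash, or (fever) a vital sign value judged clinically significant |
| Confirmed interstitial lung disease, Grade 2 | 5.5.4: both drugs end | Only if intolerable or an SAE |
| Grade 1 ficlatuzumab toxicity outside the five categories, two doses missed | 5.5.3: ficlatuzumab ends | No, unless an SAE |
| Grade 2 ficlatuzumab toxicity outside the five categories, two doses missed | 5.5.3: ficlatuzumab ends | Only by investigator judgment or as an SAE |
| Grade 2 thrombocytopenia that does not recover | Table 4A: ficlatuzumab held; reduction comes only after recovery | Only if clinically significant, intolerable or an SAE |
| Intolerable Grade 2 edema | Table 4B: ficlatuzumab held, then reduced | Yes, by criteria 3 and 6 |
| Table 4A and 4B hold rows at Grade 3 or higher | Held, reduced or stopped | Yes, by criterion 1 |

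The first row is the clearest. For Grade 1 and Grade 2 infusion reactions Table 6 keeps the cetuximab dose and halves the rate, so the first reaction involves no dose reduction. The second reaction at the slower rate then ends the drug. Going through the criteria for a non-serious Grade 1 second reaction without rash:

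- It is below Grade 3 and is not an SAE.
- It is not Grade 2, so neither Grade 2 route applies.
- No dose was reduced.
- It is not in a named category.

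It therefore meets none of the six. The first reaction, if of the same kind, is not entered either, so the database could show no infusion reaction for a patient whose cetuximab was stopped for two of them.

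The fourth row is reachable but less likely, because no row of Table 4A or 4B holds ficlatuzumab for a Grade 1 event. It would take two doses skipped outside those tables.

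Section 5.4.1 also lists unacceptable AEs as a reason to end treatment, with no grade stated, and this is not an entry criterion. The combined AST/ALT and bilirubin stopping row in Table 4B was left out, because the documents do not give the CTCAE cut-offs needed to grade it.

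**The case against.** Selective AE entry is a legitimate choice, and most events that matter are already entered. The hold rows in Tables 4A and 4B are nearly all Grade 3 or higher, and many resume at a reduced level, which meets the dose-reduction criterion. The exceptions are edema, entered twice over, and Grade 2 platelet counts, which have the clinical-significance route. Confirmed interstitial lung disease is a strong candidate for an important-medical-event SAE under Section 12.1. Rash is part of both the Grade 1 and Grade 2 infusion reaction definitions and is entered at any grade. Patients with a prior severe infusion reaction are excluded. All AEs are to be recorded in any case, and ending treatment for an unacceptable AE is a listed reason with its own follow-up (Section 5.4.4).

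Most of this stands, and it limits the point. It does not remove it. The Grade 1 infusion reaction case has no route in. The Grade 2 routes rest on opinion where an objective fact, that the drug was stopped, is available. The statement that all AEs are recorded does not settle what reaches the database, because the sentence restricting entry follows it; the two need reconciling. The end-of-treatment reason does not help when only one drug stops in Arm B and the other continues, as Section 5.5.2 allows.

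A reader might infer more than the documents support:

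- *That Grade 1–2 discontinuations are missed in general.* Those that are serious, intolerable, clinically significant Grade 2 values or in the five categories are entered.
- *That the loss is larger in Arm B.* Arm B has the extra drug and the infusion reaction rule, but no rate is given for either arm.
- *That about 3 percentage points are lost.* With the 33 to 37 patients per arm implied by Section 10.3 (66/2 and 74/2), one patient is 1/33 = 3.0% or 1/37 = 2.7%. That is the weight of one patient at full accrual, not an estimate of loss. The plan specifies no discontinuation proportion, and an arm may stop as early as 8 patients (Section 10.7).
- *That the choice of arm is affected.* The design is non-comparative, and Section 10.3 advances an arm on PFS alone.

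**Conclusion.** The concern holds in a limited form. The entry list has no trigger for an AE that holds or ends a drug. The omission is certain for non-serious Grade 1 events outside the five categories and judgment-dependent at Grade 2. How often it happened is unknown; it is probably small, and the documents give no rate from which to calculate it. What is affected is the completeness of the toxicity description, not the primary endpoint or the selection rule.

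The conclusion assumes that sites applied the restricting sentence as written. If they entered every recorded AE, nothing was lost and only the wording needs attention.

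**What to change.** - In Section 12.2, widen the treatment-action criterion so that any-grade AEs leading to a hold or skipped dose, or to permanent discontinuation, of either drug are entered along with those leading to a dose reduction. This matches the existing action-taken fields.
- Reconcile the criterion with the statement in the same section that all AEs must be recorded, saying what stays in site source and what goes into the database.
- Tabulate AEs leading to discontinuation of each drug, by arm.
- Ficlatuzumab dosing ended by March 31, 2021 (Sections 5.1 and 5.4.1) and this version is dated 05/23/2023, so new wording cannot change capture during ficlatuzumab dosing. Check drug-stop and skipped-dose records against the AE database, back-fill from site source records, and disclose any gap that remains in the report.

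The cost is a few extra AE entries and a limited source check. No dose, hold or stopping rule is altered.

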12.3 Reporting of Serious Adverse Events

All Serious Adverse Events as defined in Section 12.1 will be collected starting Cycle 1, Day 1 and must be reported to the Sponsor. SAEs will be followed per the details indicated in protocol Section 8.5.1. SAEs must be reported to the IRB of Record per local procedure.

Regardless of attribution, SAEs must be reported to the sponsor and the UACC DSMB within 24 hours of notification of the event. SAEs will also be copied to the Aveo pharmacovigilance entity, Parexel. The FiclaYCetux Serious Adverse Event Report Form must be used to report SAEs and redacted, relevant medical records must be attached when available. Follow-up information that describes an increase in severity or risk must be submitted within 24 hours of notification of the information. Follow-up SAE reports must also be reported within 24 hours of notification of updated information related to the event.

The Sponsor, UACC DSMB, and/or the Aveo pharmacovigilance entity, Parexel, may contact site personnel with queries to ensure all necessary information is obtained.

SAEs must be recorded in the OnCore "SAEs" tab.

12.4 Review of Safety Information: Sponsor-Investigator Responsibilities

The sponsor will review all SAEs and safety information received to determine if the events meet the reporting requirements for FDA. Information will be reviewed and reported, if needed, by the Sponsor-Investigator consistent with 21 CFR 312.32 IND safety reporting.

12.5 IND safety reports for ficlatuzumab

Suspected, Unexpected, and Serious Adverse Drug Reaction (SUSAR)/IND Safety reports received from Aveo will be distributed to site investigators within 15 days of receipt. Any updates to the ficial fiction and Investigator Brochure will be distributed upon receipt from Aveo.

13. DATA HANDLING AND RECORD-KEEPING

Local site PIs are responsible to maintain, archive, and retain research records according to local and Federal policy, and per the Clinical Trial Agreement. This includes, but is not limited to, accurate drug accountability and disposition records, case histories, and source documents.

The Sponsor-Investigator will maintain records in accordance with Good Clinical Practice guidelines.

The Sponsor-Investigator will retain the specified records and reports for up to 2 years after the marketing application is approved for the investigational drug; or, if a marketing application is not submitted or approved for the investigational drug, until 2 years after investigations under the IND have been discontinued and the FDA so notified.

14.ETHICS AND REGULATORY COMPLIANCE

14.1 Institutional Review Board (IRB) approval

The Sponsor-Investigator will obtain, from the University of Arizona (UA) Institutional Review Board (IRB), prospective approval of the clinical protocol and corresponding informed consent form(s); modifications to the clinical protocol and corresponding informed consent forms, and advertisements (i.e., directed at potential research subjects) for study recruitment. Once UA IRB approval is secured, the revised materials will be distributed to each participating site. Each site participating in the trial must obtain IRB approval from the applicable IRB prior to initiating the research.

The only circumstance in which a deviation from the current IRB-approved clinical protocol/consent form(s) may be initiated in the absence of prospective IRB approval is to eliminate an apparent immediate hazard to the research subject(s). Per local procedure, investigators must promptly notify the applicable IRB of the deviation.

The University of Arizona IRB operates in compliance with FDA regulations at 21 CFR Parts 50 and 21 CFR 56, and in conformance with applicable International Conference on Harmonization (ICH) Guidelines on Good Clinical Practice (CGP).

In the event that the University of Arizona IRB requires, as a condition of approval, substantial changes to a clinical protocol submitted under an FDA-accepted IND application, or in the event of the Sponsor-Investigator's decision to modify the previously accepted clinical protocol:

• The Sponsor-Investigator will submit (i.e., in advance of implementing the change) a Protocol Amendment to the IND describing any change to a Phase 2 or Phase 3 protocol that significantly affects the safety of subjects, the scope of the investigation, or the

scientific quality of the study. Examples of Phase 2 and 3 clinical protocol changes requiring the submission of a Protocol Amendment include:

- o Any increase in drug dosage or duration of exposure of individual subjects to the investigational drug beyond that described in the current protocol, or any significant increase in the number of subjects under study.
- o Any significant change in the design of the protocol (such as the addition or deletion of a control group).
- o The addition of a new test or procedure that is intended to improve monitoring for, or reduce the risk of, a side effect or adverse event; or the dropping of a test intended to monitor the safety of the investigational drug.

14.2 Ethical and scientific conduct of the clinical research study

The clinical research study will be conducted in accordance with the current IRB-approved clinical protocol; ICH GCP Guidelines adopted by the FDA; and relevant policies, requirements, and regulations of the University of Arizona IRB and applicable federal agencies.

14.3 Subject informed consent

The Sponsor-Investigator and local site PIs will make certain that an appropriate informed consent process is in place to ensure that potential research subjects, or their authorized representatives, are fully informed about the nature and objectives of the clinical study, the potential risks and benefits of study participation, and their rights as research subjects. The site PIs or a sub-investigator(s) designated appropriately, will obtain the written, signed informed consent of each subject, or the subject's authorized representative, prior to performing any study-specific procedures on the subject. The date and time that the subject, or the subject's authorized representative, signs the informed consent form and a narrative of the issues discussed during the informed consent process will be documented in the subject's case history. Each site will retain the original copy of the signed informed consent form, and a copy will be provided to the subject, or to the subject's authorized representative.

The site Pls/sub-investigators will make certain that appropriate processes and procedures are in place to ensure that ongoing questions and concerns of enrolled subjects are adequately addressed and that the subjects are informed of any new information that may affect their decision to continue participation in the clinical study. In the event of substantial changes to the clinical study or the risk-to-benefit ratio of study participation, a revised informed consent will be presented to each enroll subjects for their consideration regarding continued participation in the clinical study. A subject can withdraw from the study at any time.

15.1 Appendix A: FACT-H&N Symptom index (FHNSI)

| Subject ID: | Subject Initials: | Date Completed: |
|-------------|-------------------|-----------------|
|-------------|-------------------|-----------------|

FACT/NCCN HNSI

Below is a list of statements that other people with your illness have said are important. Please circle or mark one number per line to indicate your response as it applies to the past 7 days.

| | l | Not at all | A little bit | Some- what | Quite a bit | Very much |
|--------|--|---------------|-----------------|---------------|----------------|--------------|
| GP4 | I have pain | 0 | 1 | 2 | 3 | 4 |
| GP1 | I have a lack of energy | 0 | 1 | 2 | 3 | 4 |
| HAN7 | I can swallow naturally and easily | 0 | 1 | 2 | 3 | 4 |
| HAN 12 | I have pain in my mouth, throat or neck | 0 | 1 | 2 | 3 | 4 |
| HAN3 | I have trouble breathing | 0 | 1 | 2 | 3 | 4 |
| HAN10 | I am able to communicate with others | 0 | 1 | 2 | 3 | 4 |
| GP2 | I have nausea | 0 | 1 | 2 | 3 | 4 |
| HAN11 | I can eat solid foods | 0 | 1 | 2 | 3 | 4 |
| GES | I worry that my condition will get worse | 0 | 1 | 2 | 3 | 4 |
| GF7 | I am content with the quality of my life right now | 0 | 1 | 2 | 3 | 4 |

| English (Universal) Version 4, Copyright 2001 | | | 22 Apr Page | ril 2020 1 of 1 |
|--|---------|---------------|----------------|--------------------|
| For Internal Use ONLY | | | | |
| Form Completed By: | Subject | Other (name): | Sign/Date: | |
| Comment, if applicable: | | | | |

15.2 Appendix B: Performance Status Criteria

| ECC | OG Performance Status Scale | Karr | nofsky Performance Scale |
|-------|---|---------|--|
| Grade | Descriptions | Percent | Description |
| | Normal activity. Fully active, able | 100 | Normal, no complaints, no evidence of disease. |
| 0 | to carry on all pre-disease performance without restriction. | 90 | Able to carry on normal activity; minor signs or symptoms of disease. |
| 1 | Symptoms, but ambulatory. Restricted in physically strenuous activity, but ambulatory and able | 80 | Normal activity with effort; some signs or symptoms of disease. |
| I | to carry out work of a light or sedentary nature (e.g. , light housework, office work). | 70 | Cares for self, unable to carry on normal activity or to do active work. |
| 2 | In bed <50% of the time. Ambulatory and capable of all | 60 | Requires occasional assistance, but is able to care for most of his/her needs. |
| 2 | self-care, but unable to carry out any work activities. Up and about more than 50% of waking hours. | 50 | Requires considerable assistance and frequent medical care. |
| | In bed >50% of the time. | 40 | Disabled, requires special care and assistance. |
| 3 | Capable of only limited self-care, confined to bed or chair more than 50% of waking hours. | 30 | Severely disabled, hospitalization indicated. Death not imminent. |
| 4 | 100% bedridden. Completely disabled. Cannot carry on any | 20 | Very sick, hospitalization indicated. Death not imminent. |
| 4 | self-care. Totally confined to bed or chair. | 10 | Moribund, fatal processes progressing rapidly. |
| 5 | Dead. | 0 | Dead. |

